We propose a RCT of TF-CBT that builds on our feasibility study, with the goal of testing the effectiveness of an intervention that is locally feasible, acceptable, and holds promise for improving mental health outcomes and functioning of orphaned children. Although 8 RCTs of TF-CBT have been conducted in the US, there has never been a RCT of its effectiveness in LAMICs with high prevalence of HIV. The proposed trial, to be conducted in both Moshi, TZ and Bungoma, KE ($N = 640$, with 20 TF-CBT groups provided in each region), includes: (1) a usual care control group in each region, (2) independent research interviewers; and (3) enhanced ecological validity and local responsibility by including the lay counselors from the feasibility study to assist [name] and [name] in training and supervising the lay counselors.

3C2a. Outcomes Examined. We plan to examine clinical outcomes, which include CTG, PTS, PTSD, depressive symptoms, behavioral problems, as well as any effect on the child-guardian relationship and the child's overall daily functioning (the last of these is a tool to be developed locally in the first quarter of the study; see Tables 3 & 4). We also plan to describe and examine the impact of implementation factors (e.g., TF-CBT fidelity, lay counselor knowledge gain, guardian and child attendance) on clinical outcomes. With the increasing attention given to task-shifting approaches³² and their promise for reducing the mental health treatment gap, implementation efforts that incorporate feasible methods for building greater local responsibility and sustainability are needed.

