The proposed study is a rigorous test of clinical outcomes building on a training and supervision approach employed by [name] (consultant on this study)^{33,34}, [name]^{35,76}, and others³⁵ in RCTs in other LAMICs. This approach involves local, trained lay individuals (i.e., our feasibility study lay counselors) who act as the direct treatment model supervisors, under supervision themselves, by TF-CBT and mental health experts (i.e., [name] & [name]). Our team views this RCT as the first step in a broader research plan to test the effectiveness of TF-CBT in successive implementation stages that systematically increase local expertise and responsibility and decrease expert involvement, with the goal of enhancing our knowledge around effective, feasible, and sustainable implementation strategies in LAMICs. As stated in the recently released NIH/PEPFAR RFA, focused on HIV/AIDS specifically (i.e., RFA-AI-11-003): "scientific advances regarding the implementation of effective interventions have not kept pace."

3C2b. The comparison group for the RCT is a "usual care" (UC) condition (i.e., existing orphan support services; (see Section 3C3c for our preliminary studies on UC in TZ & KE; also see Human Subjects). We enroll 320 child-guardian dyads in each of the two conditions (TF-CBT & UC; 640 total), with half of the participants enrolled in TZ and half in KE (see Table 2). Both sites are mixed urban and rural areas, allowing testing of TF-CBT in both settings to examine any impact of setting variables (i.e. differences in UC; urban vs. rural) on clinical outcomes or implementation (e.g., fidelity, attendance). Equal numbers of males and females, and children in age groups 7-10 and 11-13 will be recruited for both TF-CBT and UC. In the POFO study we easily recruited nearly twice this number (e.g., 560) in each region, indicating that the population of OAC in the areas in which we plan to recruit are high enough to support the proposed sample.

Sample size estimates for the RCT were determined using effect sizes from TF-CBT RCTs conducted in the US^{81,104}, from outcomes obtained in our TZ feasibility trial, and data from the Zambia TF-CBT feasibility trial (see Section 3C5b; for Power Analyses). Each site has a local UC group to enhance internal validity, given unique cultural, historical, political, religious, and ethnic differences, including relatively recent election riots experienced in KE.

	Moshi, TZ		Bungoma, KE	
	Urban	Rural	Urban	Rural

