TF-CBT	80	80	80	80
Usual Care	80	80	80	80
Total by Country	320		320	
Total	640			

3C3. Study Conditions

3C3a. TF-CBT Condition. Children will receive the TF-CBT treatment protocol as tested in the TZ feasibility study and modified for KE (see 3C1c). [name], the KE-lay counselors, KE-based investigator ([name]), and the local trainers ([name], [name], & [name]) will oversee iterative modifications of the 12-week protocol that maintain fidelity and are culturally responsive and appropriate. A thorough overview of TF-CBT (Appendix D) and the TZ TF-CBT protocol (Appendix B) are included with this proposal and briefly described here. The intervention is delivered in 12 1.5-hour group sessions and 3 1-hour individual sessions, provided over 12 weeks. During weeks 1-8, guardian and child groups (8 participants in each) are run separately and concurrently with guardians and children earning the same skills. In the final 4 groups (groups 9-12) they participate in conjoint child-guardian activities. The trauma narrative, gradual exposure component is conducted in individual visits with the child (which are weekly and begin after group 4; see Appendix B), so that

the child can talk privately, one-on-one, with a counselor about the details, thoughts, and feelings related to their parent(s) death(s) and other traumatic events and so that other children are not triggered or traumatized by another child's narrative details. In groups 5-8, the children review, with counselor support, what they have done in the individual sessions (e.g., draw the picture again, write the story again), but no details are shared in the group. The group intervention is efficient (e.g., can provide treatment to 8 children-caregiver dyads with 3 counselors), culturally responsive (e.g., group delivery, modified analogies), and normalizing, as it includes other children/guardians with similar problems. The inclusion of the 3 individual sessions after trust is built, as with other group-based trauma treatment models⁹⁵ allows for individualization and privacy around specific trauma narrative details.

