3C3b. Training and Supervision of Lay Counselors. The proposed trial uses an apprenticeship model³³⁻³⁵ of implementation in which "local trainers" (i.e., the experienced lay counselors from the TZ feasibility study: [name], [name], & [name]) apprentice to the TF-CBT and mental health experts in training and supervising lay counselors. Our team will train 9 counselors in TZ and 9 counselors in KE (18 total), who will deliver 20 TF-CBT groups (10 urban; 10 rural) to 160 children in each region. Lay counselors within each region will be randomly assigned to groups (3 counselors per group; 2 lead the child group, 1 leads the guardian group), so that counselor effects are balanced across groups and setting (urban, rural). In preparation for the training, [name] and [name] will work with the local trainers to establish a training plan that allows the local trainers to pair with the TF-CBT and mental health experts in providing didactic information, modeling TF-CBT skills, and overseeing lay counselor role plays during the training. As in the feasibility study, the training will be 10 days and will include substantial opportunities for lay counselors to practice skills while receiving coaching and feedback. The training will be provided in Moshi, TZ at the end of year 1 (see Table 3), with the KE-based lay counselors and [name] travelling to Moshi to attend the training.

Lay counselors are supervised directly by the local trainers, who receive supervision and direction themselves, from [name] and [name]. Following the in-person training, the TF-CBT and mental health experts will provide training in how to set up and structure practice in supervision (during year 1) and supervision of groups (during year 2, when the intervention begins) for the lay counselors in both TZ and in KE.

We will be following established procedures used in other CBT trials that employ an apprenticeship model of CBT implementation^{33,34}. Local trainers will then provide supervision to the 18 counselors (9 in TZ, 9 in KE), while receiving weekly

ACTIVITIES	YEAR 1	YEAR 2	YEAR 3	YEAR 4	YEAR 5
Hiring					
Refine Coding Measure					
Functioning Measure Dev.					
Translation & IRB Sub					
Interviewer Training					
Local Trainer Preparation					
Lay Counselor Assessment					
Lay Counselor Training					
Lay Counselor Supervision					
Local Trainer Supervision					
Youth Enroll. & TF-CBT Groups					
Interviewer Supervision					
Youth & Guardian Assess.					

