3C4b. Assessment: Lay Counselors. In addition to clinical outcomes, we examine implementation factors that may affect clinical outcomes and, by measuring them in this RCT, we establish a benchmark for future implementation efforts. Implementation outcomes, as detailed below, include child and guardian attendance at groups (which may vary across countries; urban vs. rural settings), lay counselors' knowledge and fidelity to TF-CBT, and the lay counselor-supervisor relationship. Lay counselors will complete measures assessing knowledge and the supervisory relationship with the local trainers (see Table 4). These measures are administered to the lay counselors by the project coordinator (PC) in each site via paper and pencil self-report format and will be returned to the PC in a sealed envelope. Self-report fidelity data will involve lay counselors completing the group reports after each TF-CBT group session and emailing these reports to the local trainers and to [name] and [name], within two days of the group. Lay counselors audiorecord all sessions digitally. The electronic files are collected by the PC on a jump drive. Three child and 3 guardian sessions (6 total) will be randomly selected from each group by [name] (remotely) and will then be coded by the data entry person, who also serves as the independent coder and will be trained by Drs [name] and Cohen in TF-CBT coding procedures.

3C4c. Data Collection from Children and Guardians. As in our other research, interviewers who have experience in working with children and a college degree in a field related to data management or social services are selected. Interviewers will undergo one week of training. Interviewers receive training in issues of research confidentiality, protocols, ensuring common understanding of questions, and standard ethical procedures (see Human Subjects for more information and Appendix C for example training documents). Interviewers will not be allowed to begin interviewing until they have been certified by [name] and [name] on all procedures and passed practice interviews (see Appendix C: Interview Training Log).

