3C5c Power. Power analyses were conducted using Optimal Design 2.0¹²⁴. A primary concern when estimating power in HLM focuses on the Interclass Correlation Coefficient (ICC) for providers, as providers are nested within conditions. Higher positive ICCs result in less statistical power, and few estimates of provider ICCs for fidelity to treatment are available. A review of 20 studies predicting client functioning found provider ICCs clustering from -0.1 to .06¹²⁵. Because precise estimates for ICCs are unknown, we examined ICC thresholds within a range of effect sizes (with .05 Type I error rate, power of .80, 8 children per TF-CBT group; 320 children total). Estimates did not include the effect of covariates which, if moderately correlated with the outcome variable, will increase statistical power. Therefore, these estimates present a conservative estimate. Our primary hypothesis test (i.e. differences at 12-weeks between TF-CBT & UC) is sufficiently powered ($1-\beta = .80$) to detect small effects (.35) with ICCs up to .15, moderate effects (.50) with ICCs up to .30, and all conceivable large effects. For detecting condition differences in terms of the linear or quadratic slope, analyses suggested that the proposed *N* has power ($1-\beta = .80$) to detect effects as small as .29 on slopes. Finally, for Aim 3, the current sample of 320 individuals in the TF-CBT condition, the current study is sufficiently powered to detect small (.21) effects of individual implementation variables on outcomes, but with only 20 clusters (i.e., groups) the study will have less power to detect all but large effects of group-level variables (e.g., fidelity).

3C6. Rationale of Choices Made in the Research Design. Our team carefully considered various design and methodological challenges, our rationale for various decisions is discussed here.

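### Section 3C5c rests the Aim 3 group-level power statement on 20 TF-CBT groups when the design has 40, and it gives a primary-test total of 320 that conflicts with the trial's 640

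*Combined protocol and SAP*

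**What the plan says.** Section 3C5c describes the Aim 3 sample as "the current sample of 320 individuals in the TF-CBT condition" and continues "but with only 20 clusters (i.e., groups) the study will have less power to detect all but large effects of group-level variables". Among the inputs for its power calculations, which include the two-arm primary test at 12 weeks, it lists "8 children per TF-CBT group; 320 children total".

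The design sections give different counts:

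- 3C2 (overview): the trial has 640 participants across Moshi and Bungoma, "with 20 TF-CBT groups provided in each region".
- 3C2b: "We enroll 320 child-guardian dyads in each of the two conditions (TF-CBT & UC; 640 total"; Table 2 agrees.
- 3C3a: "guardian and child groups (8 participants in each) are run separately and concurrently".
- 3C3b: nine counselors in each country, "who will deliver 20 TF-CBT groups (10 urban; 10 rural) to 160 children in each region".
- 3C4b, on fidelity coding: "Three child and 3 guardian sessions (6 total) will be randomly selected from each group".

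Section 3C5b restricts Aim 3 to the TF-CBT condition and does not limit it to one country. Sections 3C5a and 3C5b model clustering in the TF-CBT arm only.

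**The concern.** Section 3C5c defines its clusters as groups, so 20 cannot be a count of counselors (18 in all). It pairs the full TF-CBT arm of 320 children with the number of groups in one region. That pairing implies 16 children per group, against the 8 stated in the same section and in 3C3a.

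This is the plan's only power statement for group-level variables, and fidelity is its named example. Because fidelity sessions are sampled from every group, Aim 3 should have 40 group-level fidelity values. A reader planning or interpreting that analysis would take it to be weaker than it is.

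The total of 320 listed for the primary test raises a second question: which sample size was entered. If it was not the trial's, the printed primary, slope and individual-level figures may not describe this trial.

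**Working it through.** **1. Number of groups**

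- By size: 320 / 8 = 40.
- By region: 2 × 20 = 40.
- The plan's 20 is reproduced only as one region (20 × 8 = 160 children) or with double-sized groups (320 / 20 = 16 per group).

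**2. Effect on Aim 3 group-level power**

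Fisher z, two-sided .05 (assumed), J groups treated as independent (assumed).

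Detectable r at 80% power = tanh[(1.96 + 0.84) / √(J − 3)]:

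- J = 20: tanh(2.80 / 4.12) = .59
- J = 40: tanh(2.80 / 6.08) = .43

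Power = Φ[atanh(r) √(J − 3) − 1.96]:

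| r | 20 groups | 40 groups |
|---|---|---|
| .50 | .62 | .92 |
| .40 | .42 | .73 |
| .30 | .25 | .47 |

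A simulation with 100,000 draws and a t test of r gave .64 and .92, .43 and .74, and .25 and .48.

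Independence is a best case. Each region has 20 groups × 3 counselors = 60 counselor places shared by 9 people, or about 6.7 groups each.

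**3. Primary test at 640 and at a literal 320**

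Printed thresholds at 80% power: effect .35 with ICC up to .15, and effect .50 with ICC up to .30. Section 3C5c does not state sidedness, effect-size scale or which arms were clustered, so each was varied. No dropout and no covariates; noncentral t.

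- TF-CBT arm clustered only: variance = (τ + σ²/8)/m + 1/(8m), Satterthwaite df, m = 40 groups at 640 or 20 at 320.
- Both arms clustered: variance = 4(τ + σ²/8)/J, df = J − 2, J = 80 at 640 or 40 at 320.
- Total-SD units: τ = ICC, σ² = 1 − ICC. Within-group-SD units: τ = ICC/(1 − ICC), σ² = 1.

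Example, 640, TF-CBT arm only, total SD, ICC .15: (.15 + .85/8)/40 + 1/320 = .00953; SE = .0976; .35/.0976 = 3.59; power .94.

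Two-sided power:

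| Clustering, scale | 640: .35 at .15 | 640: .50 at .30 | 320: .35 at .15 | 320: .50 at .30 |
|---|---|---|---|---|
| TF-CBT only, total SD | .94 | .99 | .70 | .86 |
| TF-CBT only, within-group SD | .92 | .97 | .65 | .75 |
| Both arms, total SD | .86 | .94 | .57 | .70 |
| Both arms, within-group SD | .80 | .84 | .50 | .54 |

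At 640 every entry reaches .80, and one-sided power is higher still. At 320 no two-sided variant reaches .80 for .35 at ICC .15; the largest ICC supported is .058. A one-sided test at 320 with TF-CBT-only clustering in total-SD units does reach it: power .80, ICC ceiling .152, and .92 for .50 at ICC .30. In within-group-SD units the one-sided figure for .35 is .76.

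**4. Which N was entered?**

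- For 640: both arms clustered, within-group SD, two-sided gives ICC ceilings of .152 and .332, near the printed .15 and .30. That is not the clustering planned in 3C5b. With the planned clustering at 640, the two-sided ceilings for .35 are .41 and .26.
- For one country (160 TF-CBT children in 20 groups plus 160 usual care): the detectable individual-level correlation, tanh[2.80 / √(n − 3)], is .22 at n = 160 and .16 at n = 320. The printed figure is .21.

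Neither match is proof. The slope figure of .29 was not checked, because the plan does not give the inputs for it.

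**The case against.** The cluster count has no good defence: no other section repairs it. The case on the other side concerns how much follows from it.

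- **The caveat barely changes.** The printed wording is qualitative, and with 40 groups power is still below .80 at r = .40 and r = .30. This stands. So does the point that shared counselors make the gain a best case. A reader might infer that fidelity effects become well powered once the count is corrected; the figures do not support that for smaller effects.
- **The total of 320 may be harmless or deliberate.** Section 3C5c itself uses 320 for the TF-CBT arm, so a mislabel is plausible. So is a one-country input, since 320 in total, 8 per group and 20 groups fit together as one country and .21 fits n = 160 better. Against the one-country reading, 3C5c attaches 320 to the TF-CBT condition. The documents do not decide, so simply relabelling 320 as the TF-CBT arm would presume the answer.
- **A literal 320 does not rule out the printed thresholds.** Hypothesis 1 is directional and sidedness is not stated; one one-sided variant meets both. This stands, so the statement that 320 fails for .35 at ICC .15 is confined to two-sided tests.

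**Conclusion.** Section 3C5c is wrong on the cluster count: 40 TF-CBT groups, not 20. The Aim 3 group-level statement understates power, with a detectable correlation of about .59 as stated against about .43 by design, assuming a two-sided .05 test and independent groups. The error is conservative.

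The primary-test total of 320 conflicts with 640, and its origin is unresolved. A reader might infer that the primary test is underpowered. The documents do not support that: at the enrolled 640 both printed thresholds are met in every variant tried, without dropout. The strictest variant (both arms clustered, within-group SD, two-sided) has little margin: its .80 for .35 at ICC .15 falls to .79 or .76 if 10% or 20% loss is assumed. That variant is not the planned analysis.

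Severity is minor. Confidence is high for the cluster count only.

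**What to change.** In section 3C5c:

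1. Replace 20 clusters with 40 groups, then rerun and restate the Aim 3 group-level power, noting that groups share counselors.
2. State which N and cluster count were entered for the primary, slope (.29) and individual-level (.21) figures. Rerun any not based on 640 in total, 320 in TF-CBT and 40 groups.
3. State sidedness, effect-size scale, and whether clustering was in the TF-CBT arm only, as in the planned model.

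The cost is one revised paragraph, one certain rerun for Aim 3, and further reruns only if the inputs prove to differ from the design. Enrolment and analysis do not change.
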